6.6.2 Dose Modification With Lenvatinib

Lenvatinib dose reduction and interruption for participants who experience pembrolizumab + lenvatinib combination therapy-related toxicity will be in accordance with the dose modification guidelines described in Table 8. An interruption of lenvatinib for more than 28 days will require Sponsor approval before treatment can be resumed.

The starting dose of lenvatinib is 20 mg/day. Dose reductions of lenvatinib occur in succession based on the previous dose level (14, 10, 8 mg/day). Any dose reduction below 8 mg/day must be discussed with the Sponsor. Once the lenvatinib dose has been reduced, it

may not be increased at a later date, unless the dose has been mistakenly decreased; in this situation, the Sponsor's approval is required to increase the dose.

Refer to the subsections below for management of hypertension (Section 6.6.2.1), proteinuria (Section 6.6.2.2), diarrhea (Section 6.6.2.3), hepatotoxicity (Section 6.6.2.4), thromboembolic events (Section 6.6.2.5), posterior reversible encephalopathy syndrome/ reversible posterior leukoencephalopathy syndrome (PRES/RPLS; Section 6.6.2.6), hypocalcemia (Section 6.6.2.7), hemorrhage (Section 6.6.2.8), gastrointestinal perforation or fistula formation (Section 6.6.2.9), QT prolongation (Section 6.6.2.10), and ONJ (Section 6.6.2.11) as appropriate, before consulting the dose modification table (Table 8). For overlapping toxicities of pembrolizumab and lenvatinib, please refer to Section 6.6.3.

Table 8 Dose Modification Guidelines for Lenvatinib-Related Adverse Events

Treatment-Related Toxicity ^{a,b}	Management	Dose Adjustment
Grade 1 or Tolerable Grade 2		
	Continue treatment	No change
Intolerable Grade 2^{c,d} or Grade 3^{e,f}		
First occurrence	Interrupt lenvatinib until resolved to Grade 0-1, or tolerable Grade 2	Reduce lenvatinib dose to 14 mg once a day (1-level reduction)
Second occurrence (same toxicity or new toxicity)	Interrupt lenvatinib until resolved to Grade 0-1, or tolerable Grade 2	Reduce lenvatinib dose to 10 mg once a day (1-level reduction)
Third occurrence (same toxicity or new toxicity)	Interrupt lenvatinib until resolved to Grade 0-1, or tolerable Grade 2	Reduce lenvatinib dose to 8 mg orally once a day (1-level reduction)
Fourth occurrence (same toxicity or new toxicity)	Interrupt lenvatinib	Discuss with Sponsor
Grade 4^g: Discontinue Study Treatment		
AE=adverse event; BMI=body mass index; CTCAE=Common Terminology Criteria for Adverse Events. Note: For grading see CTCAE version 5.0. Collect all AE grades (ie, decreasing and increasing CTCAE grade). a. An interruption of study treatment for more than 28 days will require Sponsor approval before treatment can be resumed. b. Initiate optimal medical management for nausea, vomiting, hypertension, hypothyroidism and/or diarrhea prior to any lenvatinib interruption or dose reduction. c. Applicable only to Grade 2 toxicities judged by the participant and/or physician to be intolerable. d. Obese participants (BMI ≥30) with weight loss do not need to return to their baseline weight or within 10% of their baseline weight (ie, Grade 1 weight loss). These participants may restart study intervention at a lower dose once their weight remains stable for at least 1 week and they have a minimum BMI of 25. The new stable weight should be used as the new baseline for further dose reductions. e. For asymptomatic laboratory abnormalities, such as Grade ≥3 elevations of amylase and lipase that are not considered clinically relevant by the investigator, continuation of treatment should be discussed with Sponsor. f. For Grade 3 thromboembolic event, permanently discontinue lenvatinib/matching placebo. See Section 6.6.2.5. g. Excluding laboratory abnormalities judged to be non-life-threatening, in which case manage as Grade 3.		

6.6.2.1 Management of Hypertension

Hypertension is a recognized side effect of treatment with drugs inhibiting VEGF signaling. Investigators should therefore ensure that participants enrolled to receive treatment with lenvatinib have BP of $\leq 150/90$ mm Hg at the time of study entry and, if known to be hypertensive, have been on a stable dose of antihypertensive therapy for at least 1 week before C1D1. Early detection and effective management of hypertension are important to minimize the need for lenvatinib dose interruptions and reductions.

Regular assessment of BP should be as detailed in the SoA (Section 1.3.1 and Section 1.3.3). Hypertension will be graded using NCI CTCAE v5.0, based on BP measurements only (and not on the number of antihypertensive medications).

If the participant's first BP measurement of the current assessment is elevated (ie, systolic BP ≥ 140 mm Hg or diastolic BP ≥ 90 mm Hg), the BP measurement should be repeated at least 5 minutes later. One BP assessment is defined as the mean value of 2 measurements at least 5 minutes apart. If the BP assessment (ie, the mean of the 2 BP measurements obtained at least 5 minutes apart) is elevated (systolic BP ≥ 140 mm Hg or diastolic BP ≥ 90 mm Hg), a confirmatory assessment should be obtained at least 30 minutes later by performing 2 measurements (at least 5 minutes apart) to yield a mean value.

Antihypertensive agents should be started as soon as elevated BP (systolic BP ≥ 140 mm Hg or diastolic BP ≥ 90 mm Hg) is confirmed on 2 assessments at least 30 minutes apart. The choice of antihypertensive treatment should be individualized to the participant's clinical circumstances and follow standard medical practice. For previously normotensive participants, appropriate antihypertensive therapy should be started when systolic BP ≥ 140 mm Hg or diastolic BP ≥ 90 mm Hg is first observed on 2 assessments at least 30 minutes apart. For those participants already on antihypertensive medication, treatment modification may be necessary if hypertension persists.

Lenvatinib should be withheld in any instance where a participant is at imminent risk to develop a hypertensive crisis or has uncontrolled hypertension (eg, BP $\geq 160/100$ mm Hg) with significant risk factors for severe complications, significant risk factors for cardiac disease, intracerebral hemorrhage, or other significant co-morbidities. Once the participant has been on the same antihypertensive medications for at least 48 hours and the BP is controlled, lenvatinib should be resumed as described below.

Participants who have had systolic BP ≥ 160 mm Hg or diastolic BP ≥ 100 mm Hg must have their BP monitored every 2 weeks (or more frequently as clinically indicated) until systolic BP has been ≤ 150 mm Hg and diastolic BP has been ≤ 95 mm Hg for 6 weeks. If a repeat event of systolic BP ≥ 160 mm Hg or diastolic BP ≥ 100 mm Hg occurs, the participant must resume every 2 week evaluation until systolic BP has been ≤ 150 mm Hg and diastolic BP has been ≤ 95 mm Hg for 6 weeks.

The following guidelines should be followed for the management of systolic BP ≥ 160 mm Hg or diastolic BP ≥ 100 mm Hg confirmed on 2 BP assessments at least 30 minutes apart:

1. Continue study drug and institute antihypertensive therapy for participants not already receiving this.
2. For those participants already on antihypertensive medication, the dose of the current agent may be increased, if appropriate, or 1 or more agents of a different class of antihypertensive should be added. Study treatment can be continued without dose modification.
3. If systolic BP ≥ 160 mm Hg or diastolic BP ≥ 100 mm Hg persists despite maximal antihypertensive therapy, then lenvatinib administration should be interrupted and restarted at 1 dose level reduction only when systolic BP ≤ 150 mm Hg and diastolic BP ≤ 95 mm Hg and the participant has been on a stable dose of antihypertensive medication for at least 48 hours.
 - If systolic BP ≥ 160 mm Hg or diastolic BP ≥ 100 mm Hg recurs on the first dose reduction despite optimal management of hypertension with antihypertensive medications (either by dose increase or the addition of a different class of antihypertensive), then lenvatinib administration should be interrupted and restarted at an additional dose reduction only when systolic BP ≤ 150 mm Hg and diastolic BP ≤ 95 mm Hg and the participant has been on a stable dose of antihypertensive medication for at least 48 hours.
 - If systolic BP ≥ 160 mm Hg or diastolic BP ≥ 100 mm Hg recurs on the second dose reduction despite optimal management of hypertension with antihypertensive medications (either by dose increase or the addition of a different class of antihypertensive), then lenvatinib administration should be interrupted and restarted at a third dose reduction only when systolic BP ≤ 150 mm Hg and diastolic BP ≤ 95 mm Hg and the participant has been on a stable dose of antihypertensive medication for at least 48 hours.
 - Additional dose reduction should be discussed with the Sponsor.

The following guidelines should be followed for the management of Grade 4 hypertension (life-threatening consequences):

1. Institute appropriate medical management
2. Discontinue study drug

6.6.2.2 Management of Proteinuria

Regular assessment of proteinuria should be conducted as detailed in the SoA (Section 1.3). Guidelines for assessment and management of proteinuria are as follows:

Detection and Confirmation

1. Perform urine dipstick testing or urinalysis per the SoA (Section 1.3.1 and Section 1.3.3). Urine dipstick testing is the preferred method for testing for urinary protein, however, urinalysis may be used if the use of urine dipsticks is not feasible.
2. A 24-hour urine collection initiated as soon as possible and at least within 72 hours (or an immediate spot urine protein-to-creatinine ratio [UPCR] test) is required in the following situations:
 - The first (initial) occurrence of $\geq 2+$ (≥ 100 mg/dL) proteinuria on urine dipstick (or urinalysis) while the participant is receiving lenvatinib
 - A subsequent increase in severity of urine dipstick or urinalysis proteinuria occurring on the same lenvatinib dose level
 - When there has been a lenvatinib dose reduction and at the new dose level the urine protein dipstick result is $\geq 2+$ (≥ 100 mg/dL)
3. A 24-hour urine collection (initiated as soon as possible and at least within 72 hours) to verify the grade of proteinuria is required when UPCR is ≥ 2.4 .

Grading of Proteinuria

- Grading according to NCI CTCAE v5.0 will be based on the 24-hour urinary protein result if one has been obtained. If the participant has 4+ proteinuria by dipstick (≥ 1000 mg/dL by urinalysis), a 24-hour urinary protein result is required to confirm Grade 3 proteinuria. Management of lenvatinib administration will be based on the grade of proteinuria according to [Table 8](#).

Monitoring

- Urine dipstick or urinalysis testing for participants with proteinuria $\geq 2+$ (≥ 100 mg/dL) should be performed every 2 weeks (or more frequently as clinically indicated) until the results have been 1+ (30 mg/dL) or negative for 6 weeks.
- Proteinuria monitoring can be performed at the local laboratory or investigator site, but must be managed by the site physician.
- In the event of nephrotic syndrome, lenvatinib must be discontinued.

6.6.2.3 Management of Diarrhea

An antidiarrheal agent should be recommended to the participant at the start of study treatment, and participants should be instructed and educated to initiate antidiarrheal treatment at the first onset of soft bowel movements. The choice of anti-diarrheal agent should be individualized to the participant's clinical circumstances and follow standard medical practice. If signs/symptoms of diarrhea persist despite optimal medical management, instructions contained in [Table 8](#) should be followed.

Diarrhea is a known overlapping toxicity between pembrolizumab and lenvatinib (Section 6.6.3). If the causative agent is unknown, investigators should refer to both [Table 7](#) and [Table 8](#) for possible supportive care guidelines to follow.

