6.5.1 Rescue Medications and Supportive Care

Participants should receive appropriate supportive care measures as deemed necessary by the treating investigator. Suggested supportive care measures for the management of AEs with potential immunologic etiology are outlined along with the dose modification guidelines in Section 6.6. Where appropriate, these guidelines include the use of oral or IV treatment with corticosteroids, as well as additional anti-inflammatory agents if symptoms do not improve with administration of corticosteroids. Note that several courses of steroid tapering may be necessary as symptoms may worsen when the steroid dose is decreased. For each disorder, attempts should be made to rule out other causes such as metastatic disease or bacterial or viral infection, which might require additional supportive care. The treatment guidelines are intended to be applied when the investigator determines the events to be related to pembrolizumab.

Note: If after the evaluation of the event, it is determined not to be related to pembrolizumab, the investigator does not need to follow the treatment guidance. Refer to [Table 6](#) in Section 6.6.1 for guidelines regarding dose modification and supportive care.

It may be necessary to perform conditional procedures such as bronchoscopy, endoscopy, or skin photography as part of evaluation of the event.

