6.6.1 Immune-Related Events and Dose Modification (Withhold, Treat, Discontinue)

Dose Modification and Toxicity Management for Immune-related AEs Associated with Pembrolizumab

AEs associated with pembrolizumab exposure may represent an immune-related response. These irAEs may occur shortly after the first dose or several months after the last dose of pembrolizumab treatment and may affect more than one body system simultaneously. Therefore, early recognition and initiation of treatment is critical to reduce complications. Based on existing clinical study data, most irAEs were reversible and could be managed with interruptions of pembrolizumab, administration of corticosteroids and/or other supportive care. For suspected irAEs, ensure adequate evaluation to confirm etiology or exclude other causes. Additional procedures or tests such as bronchoscopy, endoscopy, skin biopsy may be included as part of the evaluation. Dose Modification and Toxicity Management Guidelines for irAEs associated with pembrolizumab monotherapy, coformulations, or IO combinations are provided in [Table 6](#).

Table 6 Dose Modification and Toxicity Management Guidelines for Immune-related Adverse Events Associated with Pembrolizumab Monotherapy, Coformulations or IO Combinations

General instructions: 
 Severe and life-threatening irAEs should be treated with IV corticosteroids followed by oral steroids. Other immunosuppressive treatment should begin if the irAEs are not controlled by corticosteroids. Pembrolizumab monotherapy, coformulations or IO combinations must be permanently discontinued if the irAE does not resolve or the corticosteroid dose is not ≤ 10 mg/day within 12 weeks of the last treatment. The corticosteroid taper should begin when the irAE is \leq Grade 1 and continue at least 4 weeks. If pembrolizumab monotherapy, coformulations or IO combinations have been withheld, treatment may resume after the irAE decreased to \leq Grade 1 after corticosteroid taper. 				
irAEs	Toxicity Grade (CTCAE v5.0)	Action With Pembrolizumab Monotherapy, Coformulations or IO Combinations	Corticosteroid and/or Other Therapies	Monitoring and Follow-up

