Pneumonitis	Grade 2	Withhold	
 Administer corticosteroids (initial dose of 1 to 2 mg/kg prednisone or equivalent) followed by taper Add prophylactic antibiotics for opportunistic infections 	
 Monitor participants for signs and symptoms of pneumonitis Evaluate participants with suspected pneumonitis with radiographic imaging and initiate corticosteroid treatment
	Recurrent Grade 2, Grade 3 or 4	Permanently discontinue		
Diarrhea/Colitis	Grade 2 or 3	Withhold	
 Administer corticosteroids (initial dose of 1 to 2 mg/kg prednisone or equivalent) followed by taper 	
 Monitor participants for signs and symptoms of enterocolitis (ie, diarrhea, abdominal pain, blood or mucus in stool with or without fever) and of bowel perforation (ie, peritoneal signs and ileus) Participants with \geq Grade 2 diarrhea suspecting colitis should consider GI consultation and performing endoscopy to rule out colitis Participants with diarrhea/colitis should be advised to drink liberal quantities of clear fluids. If sufficient oral fluid intake is not feasible, fluid and electrolytes should be substituted via IV infusion
	Recurrent Grade 3 or Grade 4	Permanently discontinue		

irAEs	Toxicity Grade (CTCAE v5.0)	Action With Pembrolizumab Monotherapy, Coformulations or IO Combinations	Corticosteroid and/or Other Therapies	Monitoring and Follow-up
AST or ALT Elevation or Increased Bilirubin	Grade 2 ^a	Withhold	
 Administer corticosteroids (initial dose of 0.5 to 1 mg/kg prednisone or equivalent) followed by taper 	
 Monitor with liver function tests (consider weekly or more frequently until liver enzyme value returned to baseline or is stable)
	Grade 3 ^b or 4 ^c	Permanently discontinue	
 Administer corticosteroids (initial dose of 1 to 2 mg/kg prednisone or equivalent) followed by taper 	
T1DM or Hyperglycemia	New onset T1DM or Grade 3 or 4 hyperglycemia associated with evidence of β -cell failure	Withhold ^d	
 Initiate insulin replacement therapy for participants with T1DM Administer antihyperglycemic in participants with hyperglycemia 	
 Monitor participants for hyperglycemia or other signs and symptoms of diabetes

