All Other irAEs	Persistent Grade 2	Withhold	
Based on severity of AE administer corticosteroids	
Ensure adequate evaluation to confirm etiology or exclude other causes
	Grade 3	Withhold or discontinue based on the event ^e		
	Recurrent Grade 3 or Grade 4	Permanently discontinue		
AE(s)=adverse event(s); ALT=alanine aminotransferase; AST=aspartate aminotransferase; CTCAE=Common Terminology Criteria for Adverse Events; DRESS=Drug Rash with Eosinophilia and Systemic Symptom; GI=gastrointestinal; IO=immuno-oncology; ir=immune-related; IV=intravenous; SJS=Stevens-Johnson Syndrome; T1DM=type 1 diabetes mellitus; TEN=Toxic Epidermal Necrolysis; ULN=upper limit of normal. Note: Non-irAE will be managed as appropriate, following clinical practice recommendations. ^a AST/ALT: >3.0 to 5.0 × ULN if baseline normal; >3.0 to 5.0 × baseline, if baseline abnormal; bilirubin:>1.5 to 3.0 × ULN if baseline normal; >1.5 to 3.0 × baseline if baseline abnormal ^b AST/ALT: >5.0 to 20.0 × ULN, if baseline normal; >5.0 to 20.0 × baseline, if baseline abnormal; bilirubin:>3.0 to 10.0 × ULN if baseline normal; >3.0 to 10.0 × baseline if baseline abnormal ^c AST/ALT: >20.0 × ULN, if baseline normal; >20.0 × baseline, if baseline abnormal; bilirubin: >10.0 × ULN if baseline normal; >10.0 × baseline if baseline abnormal ^d The decision to withhold or permanently discontinue pembrolizumab monotherapy, coformulations or IO combinations is at the discretion of the investigator or treating physician. If control achieved or ≤ Grade 2, pembrolizumab monotherapy, coformulations or IO combinations may be resumed. ^e Events that require discontinuation include, but are not limited to: encephalitis and other clinically important irAEs (eg, vasculitis and sclerosing cholangitis).				

Dose Modification and Toxicity Management of Infusion Reactions Related to Pembrolizumab

Pembrolizumab may cause severe or life-threatening infusion reactions including severe hypersensitivity or anaphylaxis. Signs and symptoms usually develop during or shortly after drug infusion and generally resolve completely within 24 hours of completion of infusion. Dose modification and toxicity management guidelines on pembrolizumab associated infusion reaction are provided in [Table 7](#).

Table 7 Pembrolizumab Infusion Reaction Dose Modification and Treatment Guidelines

NCI CTCAE Grade	Treatment	Premedication at Subsequent Dosing

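### Section 6.6.2.3 sends diarrhea of unknown cause to Table 7 (infusion reactions), but the immune-related diarrhea and colitis guidance is in Table 6

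*Combined protocol and SAP*

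**What the plan says.** Section 6.6.2.3 deals with diarrhea during lenvatinib treatment. It asks for antidiarrheal treatment at first onset, sends persistent cases to Table 8, notes that both drugs can cause diarrhea (with a pointer to Section 6.6.3), and ends: "If the causative agent is unknown, investigators should refer to both [Table 7](#) and [Table 8](#) for possible supportive care guidelines to follow".

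The three tables involved are these:

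- **Table 6** (Section 6.6.1) is the immune-related table. Its introduction reads "Dose Modification and Toxicity Management Guidelines for irAEs associated with pembrolizumab monotherapy, coformulations, or IO combinations are provided in" Table 6. It has a Diarrhea/Colitis row: withhold pembrolizumab at Grade 2 or 3, and discontinue permanently at recurrent Grade 3 or at Grade 4. On treatment the row says "Administer corticosteroids (initial dose of 1 to 2 mg/kg prednisone or equivalent) followed by taper". On work-up, it says of participants at Grade 2 or above: "diarrhea suspecting colitis should consider GI consultation and performing endoscopy to rule out colitis".
- **Table 7** (Section 6.6.1) is titled "Pembrolizumab Infusion Reaction Dose Modification and Treatment Guidelines". The text before it reads "Dose modification and toxicity management guidelines on pembrolizumab associated infusion reaction are provided in" Table 7.
- **Table 8** (Section 6.6.2) sets lenvatinib interruptions and reductions. Its one mention of diarrhea is note b: "Initiate optimal medical management for nausea, vomiting, hypertension, hypothyroidism and/or diarrhea prior to any lenvatinib interruption or dose reduction".

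**The concern.** When diarrhea appears on this combination, the site may not know whether it is a lenvatinib effect or immune-mediated colitis. The last sentence of Section 6.6.2.3 is written for that situation, and it is the only sentence that names tables for diarrhea of unknown cause. It should send the reader to one pembrolizumab table and one lenvatinib table. The pembrolizumab table it names is the wrong one.

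An investigator who follows the sentence literally reads about stopping an infusion and premedicating, and does not reach the grade thresholds for withholding pembrolizumab, the steroid dose or the endoscopy advice. What is at stake is the clarity of a participant-safety instruction. The statistical results are not at stake.

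**Working it through.** No arithmetic applies and the plan states no figure here to reproduce. The check is a trace of the cross-reference.

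**Step 1: compare what each table holds with what the sentence needs.**

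| Table | Subject | Diarrhea content | Named in 6.6.2.3? |
|---|---|---|---|
| 6 | Pembrolizumab immune-related events | Full row: withhold, discontinue, steroid dose, GI consultation and endoscopy, fluids | No |
| 7 | Pembrolizumab infusion reactions | None: infusion rate, premedication, resuscitation | Yes |
| 8 | Lenvatinib-related events | Note b, plus the general grade rules for lenvatinib | Yes, correctly |

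The lenvatinib half of the reference is right. The pembrolizumab half is wrong.

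**Step 2: check that this is not a numbering shift or a conversion fault.** The list of tables, the captions and the text agree on what Tables 6, 7 and 8 are. Leaving out the list of tables and the captions:

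- Table 6 is cited four times in the text: once in Section 6.5.1, once in Section 6.6.1 and twice in Section 6.6.3. All four mean the immune-related table. Section 6.5.1, for example, refers the reader to Table 6 "in Section 6.6.1 for guidelines regarding dose modification and supportive care".
- Table 7 is cited twice: in Section 6.6.1, correctly, and in Section 6.6.2.3, wrongly.

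For liver enzyme elevation, another toxicity that either drug can cause, Section 6.6.3 pairs Table 6 with Table 8. That is the pairing Section 6.6.2.3 needs. The wrong number stands in the current text and not in the summary of changes.

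**Step 3: check whether another section already supplies the missing pointer.**

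- Section 6.5.1 cites Table 6, but says its guidelines are meant for events the investigator has judged related to pembrolizumab. Section 6.6.2.3 addresses the case where that judgment has not been made.
- Section 6.6.3 names diarrhea as an overlapping event. It asks for pembrolizumab to be held if the event is found at the start of a cycle. It raises an immune-related cause if interrupting lenvatinib does not help. It calls for both drugs to be interrupted and a corticosteroid started if a suspected treatment-related event is severe or worsens rapidly. It gives no diarrhea grade thresholds, steroid dose or endoscopy advice, and both of its citations of Table 6 concern ALT and AST.

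These sections narrow the gap without closing it.

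**The case against.** The strongest reply is that this is a slip in a table number with several safeguards around it:

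- Table 6 applies through Section 6.6.1 whatever Section 6.6.2.3 says.
- Section 6.6.2 sends overlapping toxicities to Section 6.6.3 before the diarrhea subsection is reached, and Section 6.6.2.3 repeats that pointer.
- Section 7.1 requires discontinuation for any treatment-related toxicity that Section 6.6 lists as a reason for it, so Table 6's permanent-discontinuation rule binds regardless.
- The faulty sentence offers the tables only as possible supportive care and does not displace the withholding rules.
- Table 7's title shows at once that it is the wrong table, and Table 6 comes just before it.

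All of this stands, and it keeps the point small. It does not make the reference correct, and Section 6.6.3 does not cite Table 6 for diarrhea.

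Three stronger readings are tempting, and the documents do not support them:

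- A reader might infer that both named tables fail because neither holds immune-colitis guidance. Table 8 is there for lenvatinib and was never meant to hold it. A correct sentence would have one such table out of two.
- A reader might infer that the protocol leaves immune-mediated colitis unmanaged. The Table 6 row is complete and in force.
- A reader might infer that Section 6.6.3 also needs a sentence saying that lenvatinib stopped for dechallenge resumes at its prior dose if the event proves to be due to pembrolizumab. That is a separate question. The text points partly the other way: Section 6.6.2 applies Table 8 to toxicity of the combination, and Section 10.3.5 says causality should in general go to the whole regimen.

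**Conclusion.** The cross-reference is wrong as written: Section 6.6.2.3 should cite Table 6 where it cites Table 7. It is an internal inconsistency in a working safety instruction and not a questionable design choice. It is worth correcting because the sentence guides care, but it sits at the low end of what should be changed.

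Its size is one wrong table number with no quantified consequence. The documents do not give the number of participants with diarrhea of unknown cause, or the number still on treatment at Amendment 04. Section 2.1.3 reports treatment-related diarrhea in 44% in the earlier Phase 1b/2 study of the combination. That shows diarrhea is common with this regimen, but a reader should not take it as a count of cases affected here, since it does not separate out events of unknown cause.

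No estimate, endpoint or analysis changes. The conclusion rests only on the table titles, their contents and the citations in the protocol, with no outside assumption.

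**What to change.** In the last sentence of Section 6.6.2.3, replace Table 7 with Table 6 and keep the reference to Table 8. Issue this by clarification letter, or include it in the next amendment. No other section needs to change for this point.

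The cost is one table number, with no new data, form or analysis. At this stage the correction helps only participants still receiving study treatment, including any in the Second Course Treatment Phase.
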